**Table 6: Retest Frequency Recommendations**

Trends Observed for Repeat Liver Function Test	Frequency for Repeat Tests
First 3 repeat tests (including test to confirm initial alert test result)	Every 48 – 72 hrs
Increasing tendency of test result	Every 48 – 72 hrs
Stabilization of test result	Once weekly
Decreasing tendency	Once weekly – every 2 weeks

Depending on the course of the liver transaminase retest results, on a case-by-case basis, a gastroenterology or hepatology consultation or additional liver biopsy for any subject with persistent evidence of liver injury might be indicated.

If a subject lives in a remote area, they can be tested locally with the results promptly communicated to the PI site. However, testing via central lab is the preferred option.

## 11. STATISTICAL CONSIDERATIONS

### 11.1. General Considerations

Statistical analysis of this study will be the responsibility of Enanta Pharmaceuticals or its designee. Details of the statistical analysis methods will be described in the statistical analysis plan (SAP) document.

Continuous endpoints will be summarized using n, mean, standard deviation, median, 25th quartile, 75th quartile, minimum and maximum values. Categorical endpoints will be summarized by the number of subjects meeting the endpoint and the percentage of subjects out of the appropriate population. The denominator will be displayed when needed. Statistical inference will be performed as appropriate. Inferential testing will be conducted using a 2-sided alpha of 0.05, unless stated otherwise.

Any change to the data analysis methods described in the protocol will require an amendment if it changes a principal feature of the protocol. Any other change to the data analysis methods described in the protocol, and the justification for making the change, will be described in the clinical study report or SAP. Changes may only be made in the SAP prior to unblinding.

### 11.3. Analysis Populations

The following analysis populations are planned:

- Safety Population (SAF): All subjects who receive at least one dose of study drug. Subjects will be included in the treatment group that corresponds to the study drug received during the study.
- Intent-to-treat (ITT) Population: ITT subjects will be considered those randomized to treatment. The ITT subjects will be analyzed according to the treatment to which they were randomized. In the event the SAF is the same as ITT, only the ITT will be reported. This will be the primary efficacy population.
- Per Protocol (PP) Population: All randomized and treated subjects that do not have major protocol deviations which could unduly influence the efficacy analysis.
- PK Population: All subjects receiving active study drug and having any measurable plasma concentration of study drug at any time point.

### 11.4. Subject Disposition and Demographic Data

The number of subjects screened, randomized, randomized and treated, randomized and not treated, in the safety population, in the ITT population, and in the PK population will be

summarized. The denominator for the calculation of percentages will be from the number of subjects randomized.

The following categories will also be summarized for subject disposition:

- Completed study drug per protocol
- Discontinued study drug early and the reason for discontinuation
- Completed the study
- Discontinued from the study early and the reason for discontinuation

Subject demographics will be summarized by randomized treatment group for all subjects in the safety population. Appropriate baseline characteristics will be included in addition to demographic characteristics. No statistical testing will be performed. Additional details will be provided in the SAP.

### **11.5. Method of Treatment Assignment**

Subjects who meet all criteria for enrollment will be randomized to blinded treatment on Day 1 in a 1:1:1 ratio to EDP-305 2 mg, EDP-305 1.5 mg, or placebo. Assignment to treatment groups will be determined by a computer-generated random sequence using an IWRS. The IWRS will be used to assign double-blind investigational product to each subject. To achieve between-group comparability the randomization will be stratified by diabetes status and use of Vitamin E and/or pioglitazone.

### **11.6. Primary Efficacy Analysis**

Logistic regression models will analyze the co-primary endpoints of (1) proportion of subjects who achieve  $\geq 1$  stage improvement in fibrosis without worsening of steatohepatitis (2) resolution of steatohepatitis without worsening of liver fibrosis as determined by liver biopsy at 72 weeks. Treatment groups will be compared for each endpoint at a 0.025 significance level. A responder will be considered any subject achieving either endpoint. The proportion of responders for each endpoint will be compared using a logistic regression model with treatment group, diabetes status and use of Vitamin E and/or pioglitazone and baseline covariate NAS as effects. The odds ratio and 97.5% confidence interval will be reported as well.

A step-down sequential testing procedure will be used to control multiplicity in testing between doses. The high dose EDP-305 group (2 mg) will be compared to placebo using a two-sided alpha of 0.025 first, and if statistically significant, the EDP-305 1.5 mg group will be compared to placebo using a two-sided alpha of 0.025. The primary efficacy analyses will be performed using the ITT population.

#### **11.6.1. Secondary Efficacy Analysis**

Secondary endpoints will be analyzed for treatment group differences. Multiple sensitivity analyses will be performed on the primary efficacy endpoints.

For categorical endpoints (e.g., proportions) a logistic regression model testing between treatment differences with terms for diabetes status and use of Vitamin E and/or pioglitazone and baseline covariate NAS included in the model. Odds ratio and the 95% confidence intervals will be reported. If convergence is encountered the Fisher's exact test will be used to test treatment group differences.

For continuous endpoints (e.g., change from baseline) an analysis of covariance (ANCOVA) model testing treatment differences with terms for baseline diabetes status and use of Vitamin E and/or pioglitazone, baseline covariate NAS, and baseline parameter of interest included in the model. A type III sum-of-squares for the least-squares means and 95% confidence intervals will be reported.

When continuous endpoints that are repeated over visits a restricted maximum likelihood-based mixed model repeated measures (MMRM) technique may be performed. The model will include treatment, baseline covariate NAS, baseline parameter, visit, treatment-by-visit interaction as fixed effects. An unstructured variance-covariance structure will be considered to model the within-patient error. If the unstructured covariance matrix results in a lack of convergence, the heterogeneous Toeplitz covariance structure should be used. The Kenward-Roger method will be used to estimate the denominator degrees of freedom. A type III sum-of-squares for the least-squares means and 95% confidence intervals will be reported.

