**Table 3: Laboratory Evaluations**

CHEMISTRY PANEL Alanine Aminotransferase (ALT/SGPT) Albumin, Serum Albumin/Globulin (A/G) Ratio (calculation) Alkaline Phosphatase, Serum Amylase Aspartate Aminotransferase (AST/SGOT) Bilirubin, Total, Indirect and Direct Blood urea nitrogen (BUN) BUN/Creatinine Ratio (calculation) Calcium, (Serum) Creatine Kinase Creatinine, Serum (and eGFR [MDRD]) Uric Acid Electrolyte Panel (Na+, K+, Cl, Bicarb.) Phosphorus Gamma Glutamyl Transferase (GGT) Globulin, Total Lactate Dehydrogenase (LDH) Lipase Protein, Total, Serum HbA1c HOMA indices Fasting Insulinemia Fasting Plasma Glucose Total Cholesterol (TC) Triglycerides (TG)
	
HEMATOLOGY PANEL Hemoglobin Hematocrit Differential WBC Count (percentage and absolute): Basophils, Eosinophils, Lymphocytes, Monocytes, Neutrophils Mean corpuscular hemoglobin (MCH) Mean corpuscular hemoglobin concentration (MCHC) Mean corpuscular volume (MCV) Platelets Red Blood Count (RBC) White Blood Cell (Count) (WBC)
 
VIRAL DETECTION FOR ENTRY CRITERIA Human immunodeficiency virus (HIV)-1, HIV-2, Hepatitis B virus (HBV) (Hepatitis B surface antigen [HBsAg]), hepatitis C virus (HCV)
 
MARKERS OF CV RISKS AND LIPIDS Triglycerides (TG) apoB Total Cholesterol (TC) High Density Lipoprotein – Cholesterol (HDL-C) Low-Density-Lipoprotein – Cholesterol (LDL-C) Total/HDL Cholesterol (CT) Ratio Adiponectin

URINALYSIS Routine urinalysis to include: Color and appearance, pH, SG, Bilirubin, Glucose, Ketones, Leukocytes, Nitrite, Occult blood, Protein, Urobilinogen, Microscopic (including RBCs and WBCs)
	
BIOMARKERS FOR NASH Cytokeratin (CK)18 GLP-1 (glucagon-like peptide-1)
 
PD MARKERS FOR FXR ACTIVITY: Fibroblast growth factor (FGF)19 Total bile acids (BAs) C4 (7<math>\alpha</math>-OH-4-cholesten-3-one)

PREGNANCY AND OTHER TESTS Serum pregnancy test Follicle-StimulatingHormone (FSH)
	
FIBROSIS AND INFLAMMATORY MARKERS ENHANCED LIVER FIBROSIS (ELF) PANEL -Hyaluronic acid (HA), -Procollagen III amino terminal peptide (PIIINP) -Tissue inhibitor of metalloproteinase 1 (TIMP-1)

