## 10. SUBJECT SAFETY MANAGEMENT

### 10.1. Individual Subject Stopping Rules

Study drug will be discontinued in subjects with elevated ALT or AST (see below) and thorough evaluation and follow-up will be performed. Study drug will be discontinued once any one of the thresholds presented below is met. No repeat test is required. Reference Baseline is defined as the mean of Screening and Day 1 values. The following study drug stopping rules are applied:

- If ALT or AST increases to  $>5\times$  Reference Baseline (and is at least  $> 5x$  ULN)
- If ALT or AST increases to  $>2\times$  Reference Baseline (and is at least  $> 3x$  ULN) AND the increase is accompanied by
  - a concomitant total bilirubin increase to  $>2\times$  Reference Baseline (and at least  $> 2x$  ULN) **OR**
  - the INR is concomitantly  $> 1.5$
- If ALT or AST increases to  $>2\times$  Reference Baseline (and is at least  $> 3x$  ULN) **AND**
  - elevations of ALT/AST are accompanied by signs or symptoms of right upper quadrant abdominal pain, anorexia, nausea, vomiting, fever, eosinophilia ( $>$  upper limit of normal of absolute eosinophilia count), and/or rash.

Refer to Section 10.2 for close monitoring guidelines for subjects who meet criteria for drug discontinuation due to elevated ALT/AST.

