-  Height to be assessed at Screening only.
-  Full physical exam (PE) at Screening, Week 12, and EOS Visit; subsequent PE should be targeted to review new signs and symptoms.
-  Vital Signs include heart rate, respiratory rate, blood pressure, and will be measured predose.
-  Safety laboratory tests include chemistry (including liver function tests), hematology, and urinalysis and should be collected predose at all visits; See Table 3 for details. eGFR will be calculated at all visits based on the MDRD formula. HbA1c will be obtained at Screening, Baseline, week 12, and Week 72..
-  Pruritus scales (up to 2 scales) will be utilized to measure pruritus for every subject regardless of whether or not a subject experiences pruritus. Please refer to Section 8.3.5 and additional details included in the study binder.
-  QoL includes SF-36 and CLDQ-NASH. In addition, Dermatology Life Quality Index (DLQI) will be completed at each in-clinic visit by subjects who reported pruritus until resolution. Additional details can be found in the study binder.
-  Lipids and CV risk markers to be collected are detailed in Table 3.
-  Markers of inflammation include fibrinogen, CRP, IL-6, IL-1 $\beta$ , TNF- $\alpha$ , TNF- $\beta$ , alpha2 macroglobulin and haptoglobin (See Table 3).
-  One sample will be collected from all subjects predose.
-  Samples should be collected before the subject takes the daily dose of study drug. On Day 1 and Weeks 12, 36, and 72, samples should be collected predose and two samples postdose; the first postdose sample will be collected 1 to 3 hours after dosing and the second collected at least 1 hour later. At all other visits, samples will be collected only predose. If the subject took drug prior to their clinic visit, only one postdose sample should be collected.

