**Table 2: Derived variables.**

Variables	Formula
Demographic and Baseline characteristics	
Age at informed consent (in years)	$(\text{Date of informed consent} - \text{Date of birth} + 1) / 365.25$
Body mass index (BMI) (kg/m  )	$\text{Weight (kg)} / [\text{Height (m)}]^2$
Derivation of Duration	
Study day at any visit	Date of interest – Date of first dose of study drug. One day is added if this difference is $\geq 0$
Extent of exposure (Days)	Date of last randomized study drug intake – Date of first randomized study drug intake + 1
Extent of exposure (Weeks)	Extent of exposure (days)/7
Drug Compliance	
Compliance	$100 \times ((\text{Amount of drug taken}) / \text{Exposure period})$
Baseline Derivations	
Baseline	Last non-missing values collected prior to the first dose of study drug on day 1
Screening	The value obtained at screening.
Change from baseline	Post baseline value – Baseline
Percentage change from baseline	$[(\text{Change from baseline}) / \text{Baseline}] * 100$
Reference baseline	Mean of screening and day 1 value
Other Derivation	
Improvement in liver fibrosis	$\geq 1$ point decrement in fibrosis score compared to baseline
No worsening in liver fibrosis	No increment in fibrosis score compared to baseline
Resolution of liver fibrosis	If fibrosis score is 0
Improvement in NAS score	$\geq 1$ point decrement in NAS score (can occur in any of the ballooning, inflammation, or steatosis categories)

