## Final Analysis Statistical Analysis Plan (SAP)

of Vitamin E and/or pioglitazone as fixed effect along with baseline NAS score and baseline MRE value as covariate. Least-squares means (using type III sum-of-squares), standard errors, p-value and 2-sided 95% confidence interval for treatment differences will be presented for week 12 and week 72. Significance tests will be based on least-squares means using a two-sided  $\alpha = 0.05$ .

A by-subject listing will be provided for observed and derived variables.

### 8.6.3.2.4 Change from baseline in TG, total cholesterol (TC), HDL cholesterol, LDL cholesterol and adiponectin through week 72

The parameters, TG, TC, HDL cholesterol, LDL cholesterol and adiponectin are captured in lipid profile panel. All these parameters will be monitored in this study at day 1, weeks 2, 4, 8, 12, 16, 20, 24, 28, 32, 36, 40, 44, 48, 56, 64, 72 and EOS.

Observed values, change from baseline, and percentage change from baseline for the parameters triglyceride (TG), total cholesterol (TC), HDL cholesterol, LDL cholesterol and adiponectin will be summarized using an 8-number summary by visit and treatment group.

Change from baseline for each of the above parameters will be analyzed separately using a restricted maximum likelihood-based mixed model repeated measures (MMRM) technique. The model will include treatment, visit, treatment-by-visit interaction as fixed effects along with baseline NAS score and baseline value of the respective parameters as covariate. Variance-covariance structure to be used to model the within-patient error and results to be presented are described in [Section 8.6.1](#).

A by-subject listing will be provided for observed and derived variables.

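### The total cholesterol and triglyceride models leave a scheduled Screening value unused; adding it as a second covariate is a nearly free gain in precision, of a size the documents do not fix

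*Protocol*

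**What the plan says.** Protocol 11.6.1 gives the repeated-measures model one term for the parameter's own baseline: "The model will include treatment, baseline covariate NAS, baseline parameter, visit, treatment-by-visit interaction as fixed effects". SAP 8.6.3.2.4 repeats this for the lipids, "along with baseline NAS score and baseline value of the respective parameters as covariate", and the MMRM code in SAP Appendix A carries a single baseline variable.

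SAP Table 2 defines baseline as "Last non-missing values collected prior to the first dose of study drug on day 1". By schedule that is Day 1, with Screening used only if Day 1 is missing. The lipid visit list in SAP 8.6.3.2.4 also starts at Day 1: "All these parameters will be monitored in this study at day 1, weeks 2, 4, 8, 12".

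Protocol Table 3 puts TC and TG in the chemistry panel ("Fasting Plasma Glucose Total Cholesterol (TC) Triglycerides (TG") and again under cardiovascular markers and lipids. Footnote 14 of the Schedule of Assessments says: "Safety laboratory tests include chemistry (including liver function tests), hematology, and urinalysis and should be collected predose at all visits". The schedule marks these tests at both Screening and Day 1. HDL-C, LDL-C and adiponectin appear only under cardiovascular markers, whose row starts at Day 1.

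SAP Section 9, written after the study was terminated, drops adiponectin but not the other lipids, and limits output after Week 12 to summary statistics.

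**The concern.** A single TC or TG reading contains day-to-day variation as well as the subject's usual level. A second reading taken before randomisation carries further information about that level, so adjusting for both can remove residual variance from the EDP-305 versus placebo comparison. Treatment cannot affect a Screening value, so adjusting for it does not bias the comparison. The outcome and the quantity estimated stay the same.

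What is at stake is the width of the confidence intervals for two parameters under a named secondary objective (lipid profile). These are among the few inferential analyses that SAP Section 9 leaves in place, through Week 12.

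**Working it through.** **No plan figure to reproduce.** The sample-size section is redacted. The arm sizes agree with planned enrolment (3 × 112 = 336), but the documents give no standard deviation, correlation or power for any lipid. All correlations below are assumptions.

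**Set-up.** Consider one post-baseline visit with standardised values. Let r1 be the correlation of Day 1 with the outcome, r0 that of Screening with the outcome, and rb that of Screening with Day 1. Residual variance is:

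- one baseline: 1 − r1²
- two baselines: 1 − R², with R² = (r1² + r0² − 2·r1·r0·rb)/(1 − rb²)

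The gain in effective sample size is (1 − r1²)/(1 − R²) − 1. The MMRM pools several visits, so this is an approximation to it.

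**Case A: all three correlations equal to rho.** Then 1 − R² = 1 − 2rho²/(1 + rho).

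| rho | one baseline | two baselines | gain |
|---|---|---|---|
| 0.5 | 0.750 | 0.667 | 12.5% |
| 0.6 | 0.640 | 0.550 | 16.4% |
| 0.7 | 0.510 | 0.4235 | 20.4% |
| 0.8 | 0.360 | 0.289 | 24.6% |

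A simulation (4,000 trials of 112 versus 112) gave 16.1% at 0.6 and 22.9% at 0.8.

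**Case B: Screening and Day 1 closer to each other than to the outcome.** Take rb = 0.8. At r1 = r0 = 0.6, R² = (0.36 + 0.36 − 0.576)/0.36 = 0.40, and 0.64/0.60 gives 6.7%.

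| r1 | r0 = r1 | r0 5% lower | r0 10% lower |
|---|---|---|---|
| 0.5 | 3.8% | 2.1% | 0.9% |
| 0.6 | 6.7% | 3.6% | 1.6% |
| 0.7 | 12.0% | 6.4% | 2.7% |

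**Case C: as Case A, but only r0 cut by 15%.** At rho 0.5, R² = (0.25 + 0.1806 − 0.2125)/0.75 = 0.2908, and 0.75/0.7092 gives 5.8%. At rho 0.8, R² = (0.64 + 0.4624 − 0.8704)/0.36 = 0.6444, and 0.36/0.3556 gives about 1%.

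**Limit.** The gain is nil when r0 = r1·rb, that is, when Screening says nothing about the outcome beyond Day 1. An example is rb = 0.9 with r0 10% below r1.

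**In interval width.** Width scales as 1/√(1 + gain). A 12.5% gain narrows intervals by 1 − 1/√1.125 = 5.7%, and 24.6% by 10.4%. A 12% gain gives 5.5%, and a 1% gain 0.5%.

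**Cost.** At one visit the model has five terms (intercept, two treatment contrasts, NAS, baseline). At the planned 336, one more inflates variance by about (336 − 5)/(336 − 6) = 331/330 = 1.003. The cost rises with fewer subjects; the documents do not state enrolment at termination.

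**The form of adjustment matters.** If change from Day 1 stays the outcome and the Screening/Day 1 mean replaces the Day 1 covariate, Case A residual variance becomes 2(1 − rho) − (1 − rho)²/[2(1 + rho)]. At rho 0.6 this is 0.80 − 0.05 = 0.75 against 0.64, an efficiency loss of 1 − 0.64/0.75 = 15%. The simulation gave losses of 23%, 15% and 8% at rho 0.4, 0.6 and 0.8.

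**The case against.** One baseline value, the last before first dose, is ordinary practice, and the protocol and SAP apply it consistently. Nothing is biased or undefined. That is correct: this is an improvement, not the repair of an error, and a reader who inferred that the planned models are invalid would be wrong.

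The size is the weakest part. Equal correlation is doubtful, because Screening can be 70 days before Day 1 and Week 12 has a target of Day 84, so Screening and Week 12 can be about 70 + 84 = 154 days apart. A reader might infer a floor of about 8% from cutting both Screening correlations by 15%, which gives 7.9 to 10.7% for rho 0.5 to 0.8. But that also makes Screening less redundant with Day 1. Cutting only its link to the outcome (Case C) gives about 1 to 6%, so there is no such floor.

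A reader might also infer that a Screening TC and TG value is in the database for every randomised subject. The documents support only that it is scheduled. TC and TG also sit under the cardiovascular markers, which start at Day 1, and under Protocol 7.1.1.2 rescreened subjects may not repeat every assessment. A scheduled Screening draw is still the better reading, because the only chemistry test that footnote 14 limits to named visits is HbA1c. The fasting instruction in Protocol 8.4.1 is worded around dosing visits, so Screening TG may be noisier; entering it as a separate covariate lets the model give it less weight.

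Protocol 10.1 ("Reference Baseline is defined as the mean of Screening and Day 1 values") concerns liver stopping rules. It does not show that the protocol endorses two baselines for efficacy models.

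Finally, little depends on the result. Protocol 4.2.2 expects minimal lipid changes at these doses, and in the earlier phase 2 study only HDL, which cannot benefit here, differed significantly from placebo. With the study terminated, the gain is in interval width, not in subjects saved. That limits the importance of the point but does not remove it.

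**Conclusion.** The point holds as a nearly free improvement for TC and TG only. A second pre-randomisation value is scheduled, the planned models ignore it, and adding it changes neither the outcome nor the quantity estimated.

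The size rests on correlations the documents do not give: about 12 to 25% more effective subjects with equal correlations of 0.5 to 0.8, and about 1 to 12% in the less favourable patterns of Cases B and C, falling to nil in the limit. It affects two secondary endpoints through Week 12. It does not affect HDL, LDL, adiponectin or the histology endpoints.

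**What to change.** - In SAP 8.6.1, SAP 8.6.3.2.4 and the Appendix A MMRM code, and in Protocol 11.6.1, add the last Screening TC or TG value as a second covariate in the TC and TG models. Keep the Day 1 covariate and change from Day 1 as the outcome; do not substitute the Screening/Day 1 mean.
- Fill a missing Screening value without using treatment or outcome, for example with the Screening mean pooled over arms. Appendix A specifies data without imputation, so it needs this exception; otherwise subjects would be dropped. Where Day 1 is missing, the Screening value already serves as baseline and the subject stays in.
- Confirm with the central laboratory data that TC and TG were reported at Screening.
- Protocol 11.1 allows SAP changes only before unblinding. If unblinding has occurred, report this as a labelled sensitivity analysis in the study report.

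The cost is one degree of freedom in each of two models and no new data. TC and TG would then be modelled slightly differently from HDL and LDL, which the SAP should state.
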